6.0 Setting

6.1 *Describe the sites or locations where your research team will conduct the research. Consider each of the items listed below:*

- *Identify where your research team will identify and recruit potential subjects.*
- *Identify where the team will perform the research procedures.*
- *Describe the composition and involvement of any community advisory board(s).*
- *For research conducted in other locations, describe:*
 - *Site-specific regulations or customs affecting the research at those locations.*
 - *Local scientific and ethical review structure at those locations. Examples include work in other cultures or ethnic groups (within or outside of the U.S.) and work with churches. The HRPP will provide additional guidance for international research.*

Location of Recruitment:

Participants will be recruited from our REDCap data base. Previously screened participants who have agreed to be re-contacted for other studies and that meet for the current experiment will be contacted via email with an invitation to participate in the current study.

Location of study:

The entirety of data collection will be conducted online. All participants will enroll on a voluntary basis and electronically sign an IRB-approved consent form prior to study participation.

7.0 Study Intervention(s)/Investigational Agent(s)

7.1 Describe the study interventions (including behavioral interventions) and/or investigational agents (e.g., drugs or devices) to be used in this study. Consider each of the items listed below:

- *Drug/Device Handling: If the research involves drugs or devices, describe your plans to store, handle, and administer the drugs or devices so that they will be used only on subjects, and only by authorized investigators.*
- *Describe whether any of the following will be used: microwaves, X-rays, DEXA scans, general anesthesia, or sedation*
- *If control of the drugs or devices used in this protocol will be accomplished by following an established, approved organizational SOP (e.g., Research Pharmacy SOP for the Control of Investigational Drugs, etc.), please reference the SOP in this section.*

Active scarcity narrative:

"

There was a major hurricane in my area. My car and house have been destroyed by the storm. My family is depending on me to come up with a solution. The storm shelters are full of other hurricane victims and I will have to be separated from my family to get a bed. I have no idea when I will see them again or how I will get food."

Control scarcity narrative: "There was a minor storm in my area. Hail fell on both my house and car, and I have a small dent in the hood of my car. I contacted my insurance company, and the repair is fully covered. The earliest available appointment is next week, when the repair team will travel to me and fix my car while I am at work. My house appears to be undamaged."

7.2 *List the name of all drugs (including any vitamins, supplements, herbs, or nicotine) to be used in the study. Indicate whether they have FDA approval, and list any limitations for their use:*

NA

7.3 *List all devices, how they will be used, their purpose in the study, and if they will be used in a manner consistent with their approved uses. If they will be used in ways that are not yet FDA approved, indicate whether they need an IDE or a determination that they are exempt from the IDE Determination. If a determination of significant risk or non-significant risk is needed for any of the devices, include the researcher's recommendation for each of those devices:*

NA

7.4 *If the drug is investigational (has an IND) or the device has an IDE or a claim of abbreviated IDE (non-significant risk device), include the following information:*

- *Identify the holder of the IND/IDE/abbreviated IDE.*
- *Explain procedures followed to comply with sponsor requirements for FDA regulated research for the following:*

FDA Regulation	Applicable to:		
	IND Studies	IDE studies	Abbreviated IDE studies
21 CFR 11	X	X	
21 CFR 54	X	X	
21 CFR 210	X		
21 CFR 211	X		
21 CFR 312	X		
21 CFR 812		X	X
21 CFR 820		X	

NA

8.0 Procedures Involved

8.1 *Describe and explain the study design:*

Adults with alcohol use disorder will be randomly assigned to one of two scarcity narrative groups narrative (active vs. control), balanced discounting rate and sex. We will enroll approximately 160 participants in order to conclude with 112 completers (56 per group).

The procedure will include two sessions. During the first session, participants will complete all the assessments via an online survey without any independent variable. After the first session, participants will be randomized to one of two groups. During the second session, participants will be initially exposed to one of the scarcity narratives (active vs. control). They will be asked to read the narrative while also listening to the narrative on audio. They will listen to either a male or female voice. The voice will be matched based on sex. They will be asked to vividly imagine that this narrative applies to them. Next, participants will complete the assessments in the presence of these narratives.

All dependent variables will be measured pre and post exposure to the scarcity narrative for all participants. Thus, narrative effects will be measured within-subject. Comparisons between active and control narratives will conducted between groups.

8.2 *Provide a description of:*

- *All research procedures being performed*
- *If the study has more than one procedure, session, and/or subject population, describe each procedure, session, and/or study population separately. For complex studies, you are encouraged to include a figure or chart.*

Participants in our REDCap database will be contacted if they have given prior permission to be contacted for future studies. Participants will be screened again for eligibility for the current study using a Qualtrics online survey.

Eligible participants will complete two online surveys on Qualtrics. The first survey will serve as the baseline. In the second survey, they will be exposed to one of the scarcity narratives and then they will answer the survey.

8.3 *Describe:*

- *Procedures or safeguards intended to reduce the probability and magnitude of risks. (For example: Reducing the risk of injury in a virtual reality study either by having the subjects sit during the study or by providing an obstacle-free space for walking.)*
- *Be sure to describe all drugs and devices used in the research, when they will be administered or used, and their purpose.*
- *Methods used to collect data about subjects. Please upload all data collection forms to Protocol Management. Some common examples are:*
 - *Screening questionnaires*
 - *Survey(s), including online surveys*
 - *Demographic questionnaire(s)*
 - *Interview guide(s), e.g., questions or pool of questions for semi-structured interviews*
 - *Focus group guide(s)*
 - *Other documents used to collect data*

Delay Discounting: Assesses money and alcohol (matched on utility) rewards devaluation as a function of delay by presenting hypothetical choices between smaller, sooner and larger, later rewards at a range of delays.

Alcohol Purchase Task: Assesses alcohol demand, where participants report the quantity of standard alcoholic drinks they would consume across various prices.

Alcohol Relative Reinforcement Schedule: Measures substance-related and substance-free reinforcement.

Alcohol Urges Questionnaire: Assesses alcohol craving.

Alcohol Withdrawal Symptoms: Assesses alcohol withdrawal.

Temporal perception scale: Measures the subjective perception of future proximity

Contemplation Ladder: Measures readiness to change substance use

The Holmes Rahe Life Stress Inventory: Assesses occurrence of stressful life events

Obsessive Compulsive Alcohol Use Scale: Measures alcohol craving during the past week

Reward Responsiveness Scale: Assesses reward sensitivity

Stress Appraisal Measure: Assesses cognitive appraisal of an anticipatory stressful event

Expectancies and attitudes: Measures expectancies regarding intervention group membership assessed

Experiment/Experimenter Attitudes Rating Scale: Assesses participants' attitudes and a tendency to confirm arbitrary experimental hypotheses.

8.4 What data will you collect during the study and how you will obtain them? Please include descriptions of electronic data collection, database matching, and app-based data collection:

All of the survey and questionnaire data will be collected using Qualtrics, an online survey platform used to develop, administer, and collect participant data in a secure password-protected database. Only study personnel will have access to the survey and collected data.

8.5 Who will transcribe or code audio and/or video recordings?:

NA

8.6 Include a description of any deception to be used in the study. Include justification for the use of deception (why the deception is necessary), describe the debriefing process, and describe how the study meets all the following criteria for alteration of consent (deception is considered an alteration of informed consent):

- The research involves no more than minimal risk to the subjects*
- The alteration will not adversely affect the rights and welfare of the subjects*
- The research could not practicably be carried out without the alteration/deception*
- (Optional but encouraged in most cases) Subjects will be provided with additional pertinent information after participation (i.e., debriefing for studies involving deception)*

NA

8.7 *If the study involves long-term follow-up (once all research related procedures are complete), describe what data will be collected during the follow up period and when it will occur:*

NA

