5.0 Study Design and Statistical Analysis Plan

5.1 *Describe the basic study design/approach (e.g., qualitative study using five focus groups of first year students to describe assimilation into the university community; randomized controlled trial of a behavioral change intervention to increase dietary intake of whole grains; pre- post-test evaluation of new pedagogical techniques to improve adult literacy):*

The study will use a within-between design. Adults with AUD will be randomly assigned to two groups (active or control), balanced by discounting rate and sex. All participants will provide measures for all assessments pre and post exposure to the scarcity (or control) narrative.

5.2 *Describe corresponding data analysis plan/approach (e.g., content analysis of focus group transcripts; descriptive analysis followed by linear regression modeling; nonparametric analysis of pre- and post-test measures):*

Demographic characteristics will be summarized using descriptive statistics. We will compare outcome measures using a repeated measures ANOVA with active vs. control narratives as explanatory variables. Outcomes of interest include delay discounting and alcohol demand.

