authenticate their access to the two surveys of the study. They will not have to provide any PII during the surveys following the pre-screen. Throughout the remaining of the study, the only personal information linked to their ID will be their email which will be needed to send the survey links and process the payments. Data will be stored in Qualtrics and only authorized people will have access to the data in Qualtrics. If data need to be downloaded from Qualtrics, those data will be stored in password-protected folders and only the participant's ID will be included in the file. No other PII will be stored together with the participants' responses to the surveys.

9.5 Please select the identifiers you will obtain (whether directly from participants or from another source), including but not limited to:

	Name
	Geographical subdivisions smaller than a state, including street address, city, county, precinct, zip code, and equivalent geocodes (note, the initial three digits of a zip code are not considered identifiable)
	Elements of dates (except year) for dates directly related to an individual, including birth date, admission date, discharge date, date of death, and single year of age over 89 and all elements of dates (including year) indicative of such age (note, such ages and elements may be aggregated into a single category of age 90+)
	Phone numbers
	Fax numbers
	Electronic mail addresses (e-mail)
	Social Security numbers
	Medical record numbers
	Health plan beneficiary numbers
	Account numbers
	Certificate/license numbers
	Vehicle identifiers and serial numbers, including license plate numbers
	Device identifiers and serial numbers
	Web Universal Resource Locators (URLs)
	Internet protocol (IP) address numbers
	Biometric identifiers, including finger and voice prints (audio recording)
	Full face photographic images and any comparable images (including video recording)

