14.0 Number of Subjects

14.1 *Indicate the total number of subjects to be enrolled and how this number was determined (e.g., sample size calculation [show], number of available subjects in a finite pool, number of tests funding award would allow):*

In the preliminary data, we observed effect sizes ranging from $\eta^2 = .027$ to $\eta^2 = .074$. Thus, we selected a medium effect size ($f = 0.25$) to inform sample size of the current study. A total of 112 participants will complete the study (56 participants per group), assuming a type 1 error rate of 0.01 to account for multiple comparisons, 95% statistical power, and pre- and post-measure correlation of 0.25, based on an ANOVA comparing the intervention at sessions 1 and 2.

We anticipate a 70% retention rate; thus, to achieve a final sample size of 112, we anticipate consenting 160 participants.

14.2 If this is a multi-site study, indicate the number of subjects to be enrolled at this site and the total to be enrolled from all sites:

NA

14.3 If applicable, indicate the number of potential subjects you expect to screen for enrollment, and the number of subjects you will need to complete the research procedures:

We cannot accurately estimate the total number of potential participants we expect to screen. However, as described above, we anticipate enrolling 160 participants in order to complete a total of 112 participants. Additionally, the first few participants enrolled in the study may be pilots.

14.4 If the study has more than one procedure, indicate the total number of subjects to undergo each procedure separately:

All participants will undergo all sessions unless they withdraw from the study.

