16.0 Withdrawal of Subjects

16.1 Describe circumstances under which you anticipate subjects could be withdrawn from the research without their consent:

Participants may be withdrawn from the research without their consent if they become ineligible based on inclusion/exclusion criteria or learning of a contraindication for continuing, or if they demonstrate inconsistent responding during baseline assessment.

16.2 If applicable, describe any procedures for orderly termination (e.g., discontinuation of a study drug or debriefing after a behavioral intervention):

If a participant is withdrawn from the study, he or she will be informed that we have collected all the data required from their participation. If a participant is withdrawn or voluntarily discontinue, their compensation for the study will be pro-rated accordingly.

16.3 Describe procedures that you will follow when subjects withdraw from the research, including partial withdrawal from procedures with continued data collection (e.g., participant declines to continue with regular blood draws, but continues with periodic behavioral questionnaires):

If a participant is withdrawn or discontinued, they will be withdrawn from the entire study.

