After screening, eligible participants will receive a link via email. When following the link, the first page of the survey will display the full version of the consent and participants will be asked to check a box indicating that they consent in order to continue to the survey. Participants will be told that they should feel free to discuss participation with relatives, friends, and primary care physicians. Participants will also be informed of their right to stop participating in the study at any time without penalty. ICF will also include the contact information available to them should they have any questions throughout the study.

The electronic consent will be available at the beginning of each online survey and participants will be reminded that they may stop participating in the study at any time without penalty.

Non-English Speaking Subjects

- *Indicate what language(s) other than English are understood by prospective subjects or representatives.*
- *If non-English speakers will be recruited, describe the process you will use to ensure that the oral and/or written consent information provided will be in a language that they understand.*
- *If you translate consent forms and study materials, please provide a certified translation of the form as well as the certification document.*
- *Indicate the spoken language that study personnel obtaining consent will use. Describe how you will assess fluency of personnel obtaining consent to ensure that the translation is accurate.*

NA

Waiver or Alteration of Consent Process (consent will not be obtained, required information will not be disclosed, or the research involves deception)

- *Review the “CHECKLIST: Waiver or Alteration of Consent Process (HRP-410)” to ensure you have provided sufficient information for the IRB to make these determinations (i.e., that it meets the criteria for a waiver or alteration of the consent process).*

NA

Subjects who are not yet adults (minors: infants, children, teenagers)

- *Describe the criteria that you will use to determine legal age for consent to treatments or procedures involved in the research under the applicable law of the jurisdiction in which the research will be conducted (e.g., in Virginia, individuals under the age of 18 years).*
 - *For research conducted in Virginia, review “SOP: Legally Authorized Representatives, Minors, and Guardians (HRP-013)” to determine which individuals in the state meet the definition of “minor.”*

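### Does randomising after Session 1, rather than when Session 2 is opened, harm the comparison of the narratives?

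*Combined protocol and SAP*

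**What the plan says.** Session 1 is a pure baseline: "participants will complete all the assessments via an online survey without any independent variable" (section 8.1). The same section continues: "After the first session, participants will be randomized to one of two groups". The narrative, active or control, opens Session 2. Section 5.1 gives the allocation rule: "Adults with AUD will be randomly assigned to two groups (active or control), balanced by discounting rate and sex". Section 14.1 sets the numbers: "We anticipate a 70% retention rate; thus, to achieve a final sample size of 112, we anticipate consenting 160 participants". It does not divide the loss into parts before and after randomisation.

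Two other provisions bear on who reaches the narrative. Section 16.1 allows withdrawal without consent on several grounds, among them "or if they demonstrate inconsistent responding during baseline assessment". Section 24.1 states: "The electronic consent will be available at the beginning of each online survey". No section fixes the exact moment of assignment within the interval after Session 1.

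**The concern.** When an intervention starts later than randomisation, people can drop out in between. They belong to the randomised set but have received nothing and have no outcome. Three routes out exist here: not returning for Session 2, withdrawal for poor baseline responding, and declining at the Session 2 consent page.

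The arms are deliberately balanced on sex and on discounting rate, and change in discounting is a primary endpoint. Section 5.2 describes a repeated measures ANOVA with the narrative group as its only explanatory variable, so balance at assignment is the only stated control of chance baseline differences. Loss after assignment would undo part of that balance and some of the precision it brings. Assignment at the opening of Session 2 seems to avoid this for the price of a sentence.

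**Working it through.** **1. The plan's own figures.** Inputs from section 14.1: f = 0.25, type 1 error 0.01, power 95%, pre-post correlation 0.25, 112 completers, 70% retention. For the group-by-time interaction with two measurements:

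λ = N·f²·2/(1 − ρ) = 112 × 0.0625 × 2/0.75 = 18.67, with 1 and 110 degrees of freedom.

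The power is 95.3%, and 112 is the smallest even N that reaches 95%. Also 112/0.70 = 160. Both figures reproduce. The calculation contains no term for balancing on baseline, so N = 112 does not depend on it.

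**2. Unequal arms, worst case.** Assume 160 are randomised 80:80 and all 48 losses come between assignment and exposure, unrelated to arm. The size of one arm among the 112 is hypergeometric, with SD √(112 × ¼ × 48/159) = 2.9 and a 95% range of 50 to 62. For unequal arms, λ is multiplied by 4·n₁·n₂/N²:

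| Split | λ | Power |
|---|---|---|
| 56:56 | 18.67 | 95.3% |
| 50:62 | 18.45 | 95.1% |
| 48:64 | 18.29 | 94.9% |

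Expected power over the whole distribution is 95.29%, against 95.34% at an exact 56:56.

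**3. Lost balance on discounting.** Let L = 1 − 112/N be the share lost after randomisation, with perfect balancing at assignment. The between-arm difference in mean baseline discounting among completers has SD √((2/56)·L), in SD units. Change equals −0.75 × baseline plus a remainder with variance 1 − 0.25² = 0.9375, so the variance of the change contrast rises by the factor (0.9375 + 0.5625·L)/0.9375 = 1 + 0.6·L.

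| Randomised | L | SD of baseline difference | Variance factor |
|---|---|---|---|
| 124 | 0.10 | 0.059 | 1.06 |
| 140 | 0.20 | 0.085 | 1.12 |
| 160 | 0.30 | 0.104 | 1.18 |

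With no balancing the SD would be √(2/56) = 0.189. Simulation gave a mean contrast of 0.000 to 0.001 when the true effect is nil, so there is no bias. Using the ANOVA's own standard error, the probability of rejection at f = 0.25 is 98.4% at L = 0 and 97.6% at L = 0.30. Both exceed the 95.3% that the plan counts on.

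**4. These variance factors are an upper range.** Three reasons:
- L = 0.30 needs all 160 consented people to be randomised. Randomisation follows Session 1, so anyone lost in Session 1 never enters the randomised set.
- L includes people who break off after seeing the narrative. Later assignment does not prevent that.
- The factors apply to discounting only. For another primary outcome, suppose its baseline correlates r with baseline discounting, and its post value 0.25r. The excess variance is then 0.5625r²L/(1.5 − 0.5625r²). At L = 0.30 this is 0.5%, 1.0% and 3.1% for r = 0.2, 0.3 and 0.5 (assumed values).

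**5. Would assignment at log-in balance better?** Only if the full balancing method can run live, which the documents do not say. The simple substitute is a preloaded list with blocks of 4 within sex by discounting band. Simulated for 112 people, it gives a baseline-difference SD of 0.116, 0.094 or 0.082 with two, three or four bands. Continuous minimisation run between the sessions, followed by 10% to 30% loss, gives 0.064 to 0.106. The substitute can therefore do worse than what it replaces.

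**The case for a change.** The strongest case for the concern is that balance is a stated design feature, that the analysis in section 5.2 has no baseline covariate to replace it, and that at the extreme more than half of its benefit is lost (SD 0.104 against 0.189). With an assumed blocked scheme of four strata, the 95th percentile of the largest within-stratum difference in arm size falls from 7 to 2 if assignment is delayed. No new data are needed. Section 5.2 names no analysis set, so people randomised but never exposed have no stated place in it.

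Part of this stands. The moment of assignment is not fixed, and if the same balancing scheme could run at either moment, the later one would balance better. The comparison in step 5 sets a coarse scheme at log-in against a finer one run earlier; the coarse scheme run earlier would do worse still. But the gain has almost no effect on the result, and whether it can be had is unknown.

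The section 16.1 check adds little. It judges Session 1 responses, which precede assignment and must be scored anyway to balance on discounting, and nothing suggests that it follows assignment. A second consent decision at Session 2 is one reading of section 24.1; it comes before the narrative and so is also unrelated to its content. The missing analysis set is a separate omission that does not follow from the timing of randomisation.

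**Conclusion.** The concern does not hold. Assignment when Session 2 opens is itself assignment after the first session, so the plan does not prescribe the order objected to. Followed with earlier assignment, it still gives an unbiased comparison, no sample-size figure changes, and the cost is under one percentage point of power, even with all 30% of the loss placed after randomisation. Randomising after baseline already keeps Session 1 losses out of the randomised set.

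This rests on three assumptions: participants do not learn their arm before the narrative, and nothing in the documents suggests that they do; loss before exposure is therefore unrelated to arm; and recruitment continues until 112 complete. Naming the exact moment of assignment would be a clarification, not a correction.
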